1. An overdose of pembrolizumab that is not associated with clinical symptoms or abnormal laboratory results. For purposes of this study, an overdose of pembrolizumab will be defined as any dose of 1,000 mg or greater (≥ 5 times the indicated dose). No specific information is available on the treatment of overdose of pembrolizumab. In the event of overdose, the participant should be observed closely for signs of toxicity. Appropriate supportive treatment should be provided if clinically indicated. If an adverse event(s) is associated with (“results from”) the overdose of a Merck product, the adverse event(s) is reported as a serious adverse event, even if no other seriousness criteria are met.
2. An elevated AST or ALT lab value that is greater than or equal to 3X the upper limit of normal and an elevated total bilirubin lab value that is greater than or equal to 2X the upper limit of normal and, at the same time, an alkaline phosphatase lab value that is less than 2X the upper limit of normal, as determined by way of protocol-specified laboratory testing or unscheduled laboratory testing.*

*Note: These criteria are based upon available regulatory guidance documents. The purpose of the criteria is to specify a threshold of abnormal hepatic tests that may require an additional evaluation for an underlying etiology.

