1.2 Secondary Objectives

- 1.2.1 To identify the proportion of participants with adverse events.
- 1.2.2 To measure the proportion of patients with overall response to therapy [*i.e.*, overall response rate (ORR): complete response (CR) + partial response (PR)] as determined by RECIST v1.10 via imaging conducted at 2 (+/- 1-2 weeks) months, 4 (+/- 1-2 weeks) months, and 6 (+/- 1-2 weeks) months and thereafter, imaging at q3 months or as clinically indicated.
- 1.2.3 To measure the proportion of patients with CR or PR at 1-year post-treatment initiation.
- 1.2.4 To measure 1-year overall survival (defined as time from start of treatment until up to 1-year post-treatment initiation or death from any cause).

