6.2 General Concomitant Medication and Supportive Care Guidelines

The chemotherapy pharmacist will review all medications (concurrent use of other all other drugs, over the counter medications or alternative therapies) for interactions at the start of therapy and new medications will be reviewed if started. The study team should check a frequently-updated medical reference for a list of drugs to avoid or minimize use of.

Rescue Medications & Supportive Care

Participants should receive appropriate supportive care measures as deemed necessary by the treating investigator. Suggested supportive care measures for the management of AEs with potential immunologic etiology are outlined along with the dose modification guidelines in the protocol. Where appropriate, these guidelines include the use of oral or IV treatment with corticosteroids, as well as additional anti-inflammatory agents if symptoms do not improve with administration of corticosteroids. Note that several courses of steroid tapering may be necessary as symptoms may worsen when the steroid dose is decreased. For each disorder, attempts should be made to rule out other causes such as metastatic disease or bacterial or viral infection, which might require additional supportive care. The treatment guidelines are intended to be applied when the Investigator determines the events to be related to pembrolizumab.

If after the evaluation of the event, it is determined not to be related to pembrolizumab, the Investigator does not need to follow the treatment guidance. It may be necessary to perform conditional procedures such as bronchoscopy, endoscopy, or skin photography as part of evaluation of the event.

Participant Discontinuation Criteria

Discontinuation of study intervention does not represent withdrawal from the study.

As certain data on clinical events beyond study intervention discontinuation may be important to the study, they must be collected through the participant's last scheduled follow-up, even if the participant has discontinued study intervention. Therefore, all participants who discontinue study intervention prior to completion of the protocol-specified treatment period will still continue to be monitored in this study and participate in the study visits and procedures, unless the participant has withdrawn from the study.

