6.5 Duration of Follow-Up

Safety:

Patients will be followed for safety of the Cabozantinib/Pembrolizumab combination therapy for 100-days after the last dose of Pembrolizumab (or the combination).

Patients removed from the study treatment for unacceptable adverse event(s) will be followed until resolution or stabilization of the adverse event.

Survival:

Patients will be followed for disease progression and survival status up to 1 year post-therapy initiation or until death, whichever occurs first.

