8. DOSING DELAYS/DOSE MODIFICATIONS

Study participants will be monitored for AEs from the time of signing consent through 100-days after the date of the decision to permanently discontinue all study treatment (i.e., last dose). Participants will be instructed to notify their physician immediately for any occurring AE.

The following should be taken into consideration in decisions regarding dose modifications (reductions and/or delays) for treatment-related side effects.

Cabozantinib and Pembrolizumab have class-specific safety profiles based on their mechanism of action but may also cause AEs that overlap. For management of AEs that can be clearly attributed to Cabozantinib or Pembrolizumab, independent dose modification for either agent is allowed.

- Examples of VEGFR TKI associated AEs caused by Cabozantinib are hypertension and hand-foot syndrome.
- Examples of irAEs and common AEs caused by Pembrolizumab are fatigue,

musculoskeletal pain, decreased appetite, pruritus, diarrhea, nausea, rash, pyrexia, cough, dyspnea, constipation, pain, and abdominal pain.

- Examples of overlapping AEs are diarrhea and elevations in liver function tests.

Table 5. Dose Modifications.

Dose Level	Cabozantinib Dose	Pembrolizumab Dose
0 (starting dose)	40 mg, oral, qd	200mg, IV, Q3weeks
-1	20 mg, oral, qd	200mg, IV, Q3weeks
-2	20 mg, oral, qod	200mg, IV, Q3weeks
-3	Discontinue Cabo	200mg, IV, Q3weeks

Other allowed dose interruption for pembrolizumab

Pembrolizumab may be interrupted for situations other than treatment-related AEs such as medical / surgical events or logistical reasons not related to study therapy. Participants should be placed back on study therapy within 3 weeks of the scheduled interruption, unless otherwise discussed with the Sponsor. The reason for interruption should be documented in the patient's study record.

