9.7 Reporting and Exclusions

9.7.1 Evaluation of Toxicity

All patients who received study drug will be evaluable for toxicity and included in the safety analysis from the time of their first treatment with Cabozantinib and Pembrolizumab combination treatment.

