A copy of all 15 Day Reports and Annual Progress Reports is submitted as required by FDA, European Union (EU), Pharmaceutical and Medical Devices agency (PMDA) or other local regulators. Investigators will cross reference this submission according to local regulations to the Merck Investigational Compound Number (IND, CSA, etc.) at the time of submission. Additionally, investigators will submit a copy of these reports to Merck & Co., Inc. (Attn: Worldwide Product Safety; [contact]) at the time of submission to FDA.

Adverse events (AEs), SAEs, and other reportable safety events will be reported by the participant (or, when appropriate, by a caregiver, surrogate, or the participant's legally authorized representative). The investigator and any designees are responsible for detecting, documenting, and reporting events that meet the definition of an AE or SAE as well as other reportable safety events. Investigators remain responsible for following up AEs, SAEs, and other reportable safety events for outcome. The investigator, who is a qualified physician, will assess events that meet the definition of an AE or SAE as well as other reportable safety events with respect to seriousness, intensity/toxicity and causality.

The following list of AEs (Section 10.1) and the characteristics of an observed AE will determine whether the event requires expedited reporting to Overall PI and DSMC via the OnCore **in addition** to routine reporting.

Time Period and Frequency for Collecting AE, SAE, and Other Reportable Safety Event Information

All AEs, SAEs, and other reportable safety events that occur after the consent form is signed but before intervention allocation/randomization must be reported by the investigator if the participant is receiving placebo run-in or other run-in treatment, if the event cause the participant to be excluded from the study, or is the result of a protocol-specified intervention, including but not limited to washout or discontinuation of usual therapy, diet, or a procedure.

- All AEs from the time of intervention allocation/randomization through 30 days following cessation of study intervention must be reported by the investigator.

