11. STUDY CALENDAR

Baseline evaluations are to be conducted prior to start of protocol therapy as noted in the study calendar. In the event that the patient's condition is deteriorating, laboratory evaluations should be repeated within 48 hours prior to initiation of the next cycle of therapy.

	Pre-enrollment	Planned Cabo/Pembro Treatment *			Safety (100-days after final dose)	1-year Post Treatment Initiation	Off - Study
Assessment:	Screening	Cycle 1	Cycles 2 - 8	Cycles 9 - 17			
Visit Windows	Day -30 to -1	(± 3 days)	(± 3 days)	(± 7 days)	(+14 days)	(+14 days)	---
Informed consent	X						
Demographics, medical history	≤ 28 days						
Physical exam	≤ 14 days	X / Day 1 (C1-C8)		X / Day 1 of odd cycle	X	X	
Weight	≤ 28 days	X / Day 1 (C1-C8)			X	X	
Height	≤ 28 days	X					
ECOG PS	≤ 14 days	X / Day 1 (C1-C8)		X / Day 1 of odd cycle	X	X	
Vital signs	≤ 14 days		X / Day 1 of every cycle		X	X	
12-lead ECG	≤ 4 weeks	As clinically indicated.		As clinically indicated	As clinically indicated	As clinically indicated	
CBC w/ diff, platelets	≤ 14 days	Day 1 all cycles. Record in the eCRF: ANC, plts, Hemoglobin			X	X	
CMP	≤ 14 days	Day 1 of every cycle / only record results for the following in the eCRF: alk phos, total bilirubin, AST, ALT, albumin			X	X	
Hepatitis screening	X						
PT/INR, aPTT	≤ 14 days						
Urinalysis	≤ 14 days	X/ Day 1 of cycles 1 - 8		As clinically indicated	As clinically indicated	As clinically indicated	
Urine chemistry (UPCR)	≤ 14 days	X	Q6 weeks at clinic visit	As clinically indicated	As clinically indicated	As clinically indicated	
Pregnancy test	≤ 28 days	X					
TSH	≤ 14 days	X	Q6 weeks at clinic visit				
CA19-9	≤ 14 days	X, optional	CA19-9 may be evaluated at physician discretion per institutional standards.				

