Imaging: CT/MRI C/A/P	Within 8 weeks of treatment initiation	CT of the chest, abdomen, and pelvis or CT of the chest with MRI of the abdomen and pelvis will be performed in all subjects at screening and every 8 weeks (± 14 days) after first dose of Pembro/Cabo combination treatment for the first 6-months on-study or as clinically indicated. Upon completion of 6 months on study, these assessments will be performed every 12 weeks (± 7 days) up to 12-months post-treatment initiation. Tumor imaging will continue until either 12-months post-treatment initiation OR until radiographic disease progression per RECIST 1.1 as determined by the investigator. PR or CR per RECIST 1.1 at a given time point must be confirmed by repeat assessments ≥ 4 weeks after the criteria for response are first met.					

Correlative: Blood samples for Exosomal Lipids (optional)	
See ** below. These 7 blood draws for Exosomal Lipids are optional, and will be collected via another biospecimen sample collection protocol.
 
10cc blood in lavender-top tube w/ EDTA will be collected at the following 7 timepoints:
 
Pre-treatment baseline: i.e., predose Cycle 2 clinic visit Cycle 3 clinic visit Cycle 4 clinic visit Cycle 5 clinic visit Cycle 6 clinic visit Cycle 7 clinic visit
 
collected once monthly for 6-months (i.e., at clinic visit during Cycles 2 – 7). The first blood draw is prior to Cycle 1; the second blood draw occurs immediately prior to Cycle 2 (i.e., blood is drawn on day 1 of each cycle, up to Cycle 7).
						
Correlative: Archival Tumor (optional)	
*** If archival tissue is available, tumor tissue will be obtained via another protocol for biospecimen sample collection for correlative, patient-derived organoids. Patients enrolled on this trial will have to sign a separate consent for utilization of archival tissue.
						
Con Meds	X ¹	X ²	X ²	X ²	X ²	X ²	
Adverse Events	≤ 28 days	X	X	X	X	X	
Pembrolizumab (IV infusion)		X, q3 weeks for 8 cycles.		Could continue			
Cabozantinib (oral med)		C1 Day 1 dose given in clinic to monitor safety. C1 D2-D21 doses are taken at home.	X, Daily dose taken at home C2-C8	Could continue			
		Cabozantinib dispensed to subjects every 3 weeks.					
Cabozantinib daily dosing diary		The patient will record the daily amount of Cabozantinib taken in an oral medication log from Cycles 1-8 (i.e., C1D1 to C8D21).					

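### Section 9.5 equates serious with grade 3 or higher, which 10.1 rules out, so no SAE output is planned; separately, the 30-day and 100-day AE periods are unreconciled and the safety tables have no end date

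*Combined protocol and SAP*

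**What the plan says.** **Seriousness.** Section 9.5 tabulates the maximum grade per AE category of interest. It then promises a patient-by-patient description of serious events, with grade 3 or higher given in parentheses as the meaning of serious. Section 10.1 lists the SAE criteria: death, threat to life, inpatient admission or its prolongation, lasting disability, congenital anomaly, or another important medical event. Its text on intensity adds that an event is serious because it meets such a criterion and not because it is rated severe.

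**Period.** Section 10.1, under a heading on the time period for collecting safety information, says: "All AEs from the time of intervention allocation/randomization through 30 days following cessation of study intervention must be reported by the investigator". Other sections run longer:

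- Section 8: "Study participants will be monitored for AEs from the time of signing consent through 100-days after the date of the decision to permanently discontinue", which that section equates with the last dose.
- Section 6.5 follows patients for safety "for 100-days after the last dose of Pembrolizumab (or the combination" therapy.
- The calendar has a visit column headed "Safety (100-days after final dose", and its "Adverse Events" row is marked there and again at 1 year after treatment initiation.
- Section 6.2 wants certain clinical-event data collected through the participant's "last scheduled follow-up, even if the participant has discontinued study intervention".

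**Analysis.** The first secondary objective is "To identify the proportion of participants with adverse events". Section 9.7.1 says that treated patients are "included in the safety analysis from the time of their first treatment". It gives no end, and neither do 9.5 and 12.1.1.

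**The concern.** Severity and seriousness are different classifications, and the protocol says so itself. If the analysis section uses the name of one for the other, its narrative output misstates which patients had serious events, and a reader of the report cannot recover SAE counts from any output that section 9 plans.

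The period matters because the proportion of participants with an AE depends on how long events are counted. Section 7.3.2 notes that immune-related AEs can appear several months after the last dose, so the choice between 30 days, 100 days and an open end has some content here. If that choice is left to the time of analysis, it is made with the data in view.

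**Working it through.** The plan gives no figure to reproduce on this point. The check sets the passages side by side, with a few subtractions.

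**1. Two meanings of serious.** Compare the set that 9.5 would describe (grade 3 or higher) with the set that 10.1 defines (any SAE criterion met).

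- *In 9.5, not in 10.1.* Table 19, footnote b, in Appendix F places an AST or ALT value above 5 and up to 20 times ULN (normal baseline) at grade 3. If such a rise meets none of the outcome criteria, it is not an SAE, yet 9.5 calls it serious.
- *In 10.1, not in 9.5.* Section 10.1 counts an inpatient admission as serious even when it is only precautionary. It also makes an AE resulting from a pembrolizumab overdose an SAE when no other criterion is met. If either event is grade 1 or 2, 9.5 leaves it out of the description.
- *Size of the second group.* It is probably small. The grade 3 wording in 10.1 itself includes an indication for hospitalization, so most admissions would be graded 3 or higher. An overdose is defined as 1,000 mg or more, against a planned 200 mg clinic infusion.
- *What section 9 still shows.* In AE categories of interest, a grade 1-2 SAE enters the maximum-grade table, but nothing there identifies it as serious. No other output in section 9 uses the SAE definition.

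**2. The AE period.** Inputs: 30 days for all AEs (10.1), 100 days (6.5, 8, calendar), and a visit window of +14 days (calendar).

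- Follow-up beyond the 10.1 limit: 100 − 30 = 70 days, which is 70/100 = 70% of the post-treatment safety period.
- Position of the safety visit: from 100 − 30 = 70 to 100 + 14 − 30 = 84 days after the 10.1 limit.

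**3. Must AEs on days 31-100 be recorded?** Two further clauses bear on this.

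- The recording text in 10.1 has the investigator enter AE and SAE information on the case report forms whenever the patient is examined. The calendar schedules a physical examination at both the 100-day and the 1-year visit.
- Section 10.6 requires all AEs in routine data submissions and sets no time limit. Its only exception points to section 10.4, which contains no list of AEs.

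Read with section 8 and the calendar, these clauses support recording after day 30. The 30-day sentence sets a duty up to day 30 and does not say that recording then stops.

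**4. Analysis window.** Sections 9.7.1 and 12.1.1 fix the start at first treatment. No section fixes the end. Even with complete recording, three cut-offs remain open: 30 days, 100 days, or everything recorded, including the 1-year visit.

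**The case against.** On seriousness, the defence is that 9.5 states its meaning in parentheses, so the listing can be reproduced, and that SAEs go to the DSMC under 10.2 whatever 9.5 says. Both are true. A reader might infer that SAEs escape oversight, and the documents do not support that. The defence does not remove the conflict with 10.1, and it does not supply an SAE output in the analysis.

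On the period, the defence is stronger. The 30-day sentence stands in the same list as a 90-day limit for SAEs. Neither names a recipient, and the text that follows speaks of recording and reporting to the pembrolizumab manufacturer. Both limits may therefore be company reporting duties, compatible with longer follow-up at the site. A reader might infer that non-serious AEs on days 31-100 will be lost. The clauses in 10.1 and 10.6 on recording and routine submission point the other way, and the guidance documents for case report form completion named in 13.4.1 may settle it. A reader might also see a contradiction between the SAE windows in 10.1 and 10.3; these may be separate duties to two companies, and no contradiction is claimed.

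What remains is that the 10.1 heading concerns collection, and that nearby text also mentions reporting through OnCore and to the DSMC, so the status of the 30-day limit is not stated. The 100-day safety visit is the natural end for the tables, but an analyst has to infer it.

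**Conclusion.** Minor, in two parts.

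The first is an error as written: the meaning of serious in 9.5 conflicts with 10.1, it misclassifies in both directions, and section 9 has no output by the SAE definition. The number of events affected cannot be derived from the documents and is likely to be small, given the overlap between grade 3 and hospitalization.

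The second is secondary: a 30-day and a 100-day statement that need reconciling, and safety tables with no end date. The gap is 70 days, but that measures calendar time and not events. No loss of data is shown, and the proportion with any AE may change little. This rests on reading the recording and submission clauses in 10.1 and 10.6 as applying at the 100-day visit, as the calendar indicates.

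PFS, the sample size and the stopping rule are unaffected.

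**What to change.** 1. In 9.5, replace the sentence on serious toxicity with two listings: SAEs by the 10.1 definition, and AEs of grade 3 to 5.
2. Reconcile the AE period in 10.1 with 6.5, 8 and the calendar. The sponsor should confirm whether the 30-day and 90-day limits are company reporting duties and, if so, label them that way.
3. State in 9.5 that the safety tables cover first dose through the existing 100-day safety visit, with later events, such as those noted at the 1-year visit, listed separately.

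The cost is wording and one extra listing. If sites have been recording non-serious AEs only to day 30, there is also a little more data entry. No new visit is needed.

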10.2 MCC Expedited Adverse Event Reporting Guidelines

Investigators within MCC will report SAEs directly to the MCC DSMC per the MCC DSMC SOP and the University of Kentucky IRB reporting policy, as specified in the table in below. Use the MCC protocol number and the protocol-specific patient ID assigned during trial registration on all reports.

10.2.1 MCC Required forms and reporting structure

Study type	Expedited reporting to MCC	Expedited reporting to External Agency	Non-expedited AE	Form	IRB
IIT by MCC investigator sponsored by industry	
 Grade 3 –Unexpected AE PLUS Possibly, Probably or Definitely Related ALL Grade 4 Unless expected AND listed in protocol as not requiring reporting. ALL Grade 5 (fatal) Events 	FDA: Suspected AE that is serious and Unanticipated (not listed in IDB or consent)	OnCore and DSMC reporting only	Voluntary Medwatch 3500 for Serious and unanticipated OnCore for all AEs, including SAEs	Per SOPs

Note: A death on study requires both routine and expedited reporting, regardless of causality. Attribution to treatment or other cause must be provided.

Death due to progressive disease should be reported as **Grade 5 “Disease progression”** in the system organ class (SOC) “General disorders and administration site conditions.” Evidence that the death was a manifestation of underlying disease (e.g., radiological changes suggesting tumor growth or progression: clinical deterioration associated with a disease process) should be submitted.

10.2.2 Expedited Reporting guidelines for MCC IITs

Investigators within MCC will report SAEs directly to the MCC DSMC per the MCC DSMC SOP and the University of Kentucky IRB reporting policy.

Table 10.3.2 -- MCC Reportable AEs					
Attribution	Gr. 2 & 3 AE Expected	Gr. 2 & 3 AE Unexpected	Gr. 4 AE Expected	Gr. 4 AE Unexpected	Gr. 5 AE Expected or Unexpected
Unrelated Unlikely	Not required	Not required	5 calendar days [#]	5 calendar days	24 hours*
Possible Probable Definite	Not required	5 calendar days	5 calendar days [#]	5 calendar days	24 hours*
NOTES:					
